In the phase 3 pivotal studies, deaths, AEs, SAEs, as well as the laboratory abnormalities were generally equally distributed across placebo and pegloticase treatment groups, with the clear exception of gout flares and IRs. Pegloticase-treated subjects exhibited a higher rate of gout flares during Months 1-3 as uric acid was being acutely lowered, then a decrease in gout flares vs. placebo during Months 4-6. Despite use of prophylactic medications against hypersensitivity including administration of corticosteroids, antihistamine and acetaminophen in advance of each pegloticase infusion, IRs were seen in 22/85 (26%) of subjects receiving the 8 mg 2 week regimen. There was no specified definition of anaphylaxis in the Phase 3 protocols and there were no investigator-reported events of anaphylaxis in the Phase 3 studies with pegloticase. However, in a post-hoc review applying the NIAID/FAAN criteria (Sampson et al., 2006), it was determined that across the Phase 2 and Phase 3 program, anaphylaxis occurred in 6.5% of subjects treated with pegloticase dosed every 2 weeks. Anaphylaxis generally occurred within 2 hours after treatment. Manifestations included wheezing, peri-oral or lingual edema, or hemodynamic instability, with or without rash or urticaria. All of these events had relatively rapid resolution with the cessation of infusion.

In a post-hoc analysis, the apparent role of immunogenicity in both loss of urate lowering effect and incidence of IRs was appreciated. Only 2% of subjects with anti pegloticase antibody titers exceeding 1:2430 maintained a urate-lowering response to pegloticase compared with 63% of subjects who were treated for at least 2 months without developing high-titer antibodies ( $p < 0.001$ ) (Sundy et al., 2011). The incidence of IRs was higher among subjects who developed high-titer antibodies compared with those who had titers that did not exceed 1:2430 (60% vs 19%;  $p < 0.001$ ) (Sundy et al., 2011). In addition, most IRs occurred when sUA levels were greater than 6 mg/dL. Retrospective analyses showed that the loss of urate-lowering efficacy, as reflected by sUA of greater than 6 mg/dL, preceded a patient's first IR, whenever it occurred, in 20 (91%) of 22 subjects treated with pegloticase every 2 weeks.

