#### **9.7.1.3 Exploratory Endpoints**

#### **9.7.1.4 Pharmacokinetic and Anti-drug Antibody Endpoints**

The PK and anti-drug antibody endpoints are:

- PK of pegloticase.
- Incidence and titer of anti-PEG and anti-Uricase IgG antibodies.

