##### Exploratory Objectives

- Assess the pharmacokinetics (PK) of pegloticase.
- Assess the profile of anti-uricase antibodies and anti-polyethylene glycol (PEG) antibodies.

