#### 1.5.5 Pharmacokinetic and Anti-drug Antibody Endpoints

- PK of pegloticase.
- Incidence and titer of anti-PEG and anti-uricase IgG antibodies.

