#### 3.1.1 Reporting Conventions

The formats for the tables, listings, and figures described in this SAP will be provided in a companion document. Changes to the formats of these reports that are decided after the finalization of the SAP will not require an amendment. In addition, any additional supportive or exploratory analyses requested after SAP approval will not require amendment of the SAP. These additional analyses will be described in the CSR.

Study data from the electronic case report forms as well as relevant derived variables will be provided in subject data listings. An indication of specific listings for each data type may be indicated in the text of subsequent SAP sections. Data listings supplied as part of the CSR will be sorted by study center number concatenated with subject number, assessment dates, and time point, if collected.

The following conventions will be applied to all data presentations and analyses:

Continuous variables will generally be summarized by the number of subjects, mean, standard deviation, median, minimum, and maximum. Unless otherwise specified, the minimum and maximum values will be displayed to the same number of decimal places as the raw data, the mean and median will be presented to one extra decimal place compared to the raw data, and the standard deviation will be displayed to two extra decimal places compared to the raw data

Categorical variables will be summarized using frequencies and percentages within each category. Unless otherwise specified, the percentage will be presented in parentheses to one decimal place. Frequency and percentage values of 0 will be presented as '0' rather than '0 (0)'.

Unless otherwise specified, time to event data will be reporting using weeks as the timescale.

All summary tables will include the analysis set sample size (i.e., number of subjects).

Date variables will be formatted as DDMMYY for presentation.

Unless otherwise specified, confidence intervals (CI) will be based on two-sided 95% confidence.

If multiple assessments occur at a given post-baseline time point, the latest value will be used.

There will be no statistical testing to make an inference.

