### 3.4.3 Exploratory Endpoint Analyses

## 3.5 Analysis of Pegloticase Pharmacokinetics, Methotrexate Polyglutamates, and Anti-Drug Antibodies

### 3.5.1 Pegloticase and MTX PK

Serum samples for pegloticase PK analysis will be collected approximately 15 minutes to 2 hours after the end of infusion on Day 1; prior to infusion and approximately 15 minutes to 2 hours after the end of the infusion at Weeks 2, 6, 12 and 20. An additional PK sample will be collected at the End-of-Study (Week 24)/Early Termination Visit.

PK summaries will be done for the PK analysis set. MTX polyglutamate summaries will be done for the mITT analysis set. All results will be presented by 'as assigned' infusion duration group.

The following presentations of subject serum pegloticase concentration data covered in this SAP will be provided for pegloticase:

- A listing including subject, week/time point (actual, planned), treatment and serum concentrations. End of infusion sampling times are expressed relative to the start time of infusion.
- A table summary of serum pegloticase concentrations at each time point (n; mean, SD, coefficient of variation (CV)% calculated as  $100\% \times SD/mean$ , minimum, 25th percentile, median, 75th percentile, maximum, geometric mean and geometric CV%) will be provided for the PK analysis set. Similar tables will be produced by Month 6 sUA responder status.

Further, the mean and CV% of pegloticase concentrations will be provided by visit in the subset of subjects who are ADA positive (defined as positive for anti-PEG or anti-uricase antibodies at any visit) and ADA negative (defined as negative for both anti-PEG and anti-uricase antibodies at all visits) for each visit.

All concentrations BLQ after the first pegloticase infusion will be imputed by half of LLOQ for the analysis summaries. The number of BLQ records will be summarized. Concentrations more than 17 days after the last infusion will be excluded from the summary.

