### 3.5.2 Anti-Drug Antibodies

Immunogenicity of pegloticase will be assessed in serum samples by evaluating anti-PEG and anti-uricase IgG antibodies. Samples will be collected prior to the pegloticase infusion on Day 1 and at the Weeks 2, 6, 12, 20 and the End-of-study (Week 24)/Early Termination Visit and 3-month Post-Treatment Follow-up Visits. In the event of an AE suspected to be an IR, a serum sample will be collected at that time or at the subsequent visit for evaluation of pegloticase/PEG antibodies.

For anti-PEG IgG antibodies, using the safety analysis set, the number and percentage of subjects who meet the following criteria will be summarized by scheduled timepoint and overall:

- ADA positive at pegloticase baseline
- ADA negative at pegloticase baseline
- ADA negative at pegloticase baseline and ADA positive at post-pegloticase baseline
  - ADA positive at pegloticase baseline with increase in titer from pegloticase baseline
  - ADA negative at pegloticase baseline and ADA positive at post-pegloticase baseline or with increase in titer from pegloticase baseline (i.e. ADA positive status post-baseline)

For anti-uricase IgG antibodies, the number and percentage of subjects with ADA positive at pegloticase baseline and post-pegloticase baseline will be summarized by scheduled timepoint.

Kaplan-Meier estimates of the time to positive anti-PEG response (for subjects who were negative at baseline) or increase in anti-PEG titer (for subjects who were positive at baseline), and the time to anti-uricase response with 25th percentile, median, 75th percentile, and 95% CI, along with a Kaplan-Meier curve will be produced. Subjects who never have a positive anti-PEG response or increase in titer will be censored at the date of their last visit (3 month follow up visit, or, if the subject did not attend this visit, then whatever last visit they have on record). Antibody result from both scheduled and unscheduled visits will be included for the time to event analysis.

Anti-PEG and anti-uricase titer will be summarized descriptively with mean and CV% by study visit. Additionally, Anti-PEG titers at the last pegloticase infusion and post-treatment will be summarized for ADA positive post-baseline subjects.

All results will be presented by ‘as assigned’ infusion duration group.

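### The by-visit antibody titer summary in SAP 3.5.2 names only mean and CV%, which a few high titers can dominate; median, quartiles, range and geometric mean titer should be added

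*SAP*

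**What the plan says.** Protocol 9.7.1.4 lists as an endpoint "Incidence and titer of anti-PEG and anti-Uricase IgG antibodies", and SAP 1.5.5 repeats it. The related objective is exploratory: "Assess the profile of anti-uricase antibodies and anti-polyethylene glycol (PEG) antibodies".

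For titer level over time, SAP 3.5.2 says "Anti-PEG and anti-uricase titer will be summarized descriptively with mean and CV% by study visit". It also plans a summary of anti-PEG titers at the last infusion and after treatment in subjects who are antibody-positive after baseline, without naming statistics. Results are presented by assigned infusion-duration group. The section gives no rule for how antibody-negative samples enter a titer summary.

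SAP 3.5.1 treats pegloticase concentrations more fully. After n, mean, SD and CV% it lists "minimum, 25th percentile, median, 75th percentile, maximum, geometric mean and geometric CV"%. It defines CV% as 100% times SD over mean, and it sets values below the quantification limit after the first infusion to half that limit.

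The general default in SAP 3.1.1 reads: "Continuous variables will generally be summarized by the number of subjects, mean, standard deviation, median, minimum, and maximum".

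**The concern.** A titer is a dilution ratio, so differences between subjects are multiplicative. Protocol 7.1.2 shows the kind of value that can occur: "Only 2% of subjects with anti pegloticase antibody titers exceeding 1:2430 maintained a urate-lowering response". On such a scale an arithmetic mean weights subjects by the size of their titer. One subject in the tens of thousands counts for more than many at low titer, and the CV% then mostly reflects that subject.

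At stake is whether the by-visit table can show how titer level develops in a typical subject. The other planned antibody analyses do not give titer magnitude by visit. The gap matters somewhat more for anti-uricase, because SAP 3.5.2 has a by-timepoint titer-increase category for anti-PEG only. It also matters more in the cohorts of about 10, where a single subject can set the mean.

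**Working it through.** **Does mean signify the arithmetic mean?** SAP 3.5.1 lists the geometric mean separately from the mean and defines CV% as SD over mean. The unqualified terms in 3.5.2 therefore read as arithmetic mean and ordinary CV%.

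**Inputs.** Group sizes of about 110 (selected cohort) and about 10 (each other cohort) come from SAP 1.1.3. The plan states no titer figure, so there is none to reproduce. It also gives no titer distribution or assay dilution steps for this trial. Everything below rests on assumed titers and leaves out antibody-negative samples.

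**Illustration 1: 3-fold ladder (assumption).** Levels are 10, 30, 90, ..., 2430, 7290, 21870, 65610. Low titers are spread evenly over 10, 30 and 90.

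*n = 110, six subjects at 21870.* The 104 low titers sum to 34 × 130 + 10 + 30 = 4460. The six high titers sum to 6 × 21870 = 131220.
- Arithmetic mean = (4460 + 131220)/110 = 1233; CV 404%; median 30; geometric mean 43.
- Share of the sum from the six subjects = 131220/135680 = 97%.
- If all 104 low titers triple: mean = (13380 + 131220)/110 = 1315, up 7%. The median goes from 30 to 90 and the geometric mean from 43 to 120.
- If one low-titer subject (at 30) instead moves to 21870: mean = (4430 + 153090)/110 = 1432, up 16%. The median stays at 30 and the geometric mean goes to 45.

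One extra high-titer subject thus moves the arithmetic mean more than a tripling in everyone else.

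*n = 10, one subject at 21870.* Mean = (390 + 21870)/10 = 2226; median 30; geometric mean 58. Without that subject the mean is 390/9 = 43 and the geometric mean is 30.

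*Range.* For 2 to 22 high-titer subjects of 110, at 7290 to 65610, the high titers supply 76% to nearly 100% of the sum. The mean is about 5 (175/33) to 95 (13156/138) times the geometric mean.

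**Illustration 2: log-normal titers (assumption), s = SD of ln titer.** Relative SE of the arithmetic mean = √(exp(s²) − 1)/√n. Relative SE of the geometric mean ≈ s/√n. Variance ratio = (exp(s²) − 1)/s². The last column is simulated.

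| s | SE arithmetic, n = 110 | SE geometric, n = 110 | Variance ratio | Share of sum from top 6 of 110 |
|---|---|---|---|---|
| 1.0 | 12% | 10% | 1.7 | 26% |
| 1.5 | 28% | 14% | 3.8 | 42% |
| 2.0 | 70% | 19% | 13.4 | 58% |

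With n = 10 the same formulas give 41%, 92% and 232% for the arithmetic mean, against 32%, 47% and 63% for the geometric mean. At s = 1.0 and n = 110 the difference is small; it grows quickly with skew and in the small cohorts.

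**The case against.** **Other antibody analyses.** A reader might infer that most of the information on antibody development is lost. The documents contradict that. SAP 3.5.2 plans positivity by timepoint for both antibodies, anti-PEG titer increase, and Kaplan-Meier time to anti-PEG positivity or titer increase and to anti-uricase response. SAP 3.4.2.1 adds Month 6 response by antibody status, and SAP 3.6.3.4 adds infusion reactions by antibody status. None of these uses a mean titer. This objection stands and confines the point to titer level by visit.

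**The general default.** Under SAP 3.1.1 the median and range may appear anyway. That is possible, but the default applies only generally, 3.5.2 names its own shorter list, and the default has no quartiles or log-scale statistic.

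**Unknown skew.** The 1:2430 mark comes from a post-hoc analysis of earlier studies. Here all subjects receive methotrexate, which is intended to reduce antibodies, so the spread may be smaller. This stands: high titers can dominate the mean, but nothing shows that they will determine the result. Nor can the loss be sized as statistical power, because the plan makes no test and no comparison to which power would apply.

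**The geometric mean has weaknesses.** If negatives get a substituted value, the result depends on it. With 70% negative (assumption), using the lowest titer instead of half of it changes the geometric mean 2^0.7 ≈ 1.6-fold. It also mutes the high-titer subjects whom Protocol 7.1.2 links to lost response and more infusion reactions. Both points stand. They argue for adding statistics beside the mean and for computing the geometric mean among positives.

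**Selective absence.** Subjects stopped under the sUA criterion attend follow-up visits only (Protocol 9.3), so high-titer subjects may be missing mid-study. That affects every statistic and is not cured here, though n by visit would make it visible.

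**Conclusion.** The point holds in a narrow form. For a named endpoint on a dilution scale, the by-visit summary specifies mean and CV% only, while the same SAP gives pegloticase concentrations the statistics suited to skewed data. If titers are strongly skewed, a few subjects can dominate the by-visit mean and mask shifts in the rest, above all in cohorts of about 10. The size depends on the assumed spread: at n = 110 the relative SE of the arithmetic mean is 12% against 10% for the geometric mean under mild skew, and 70% against 19% under strong skew.

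The consequence is small. The objective is exploratory, nothing is tested, and neither the choice of cohort nor the primary criterion uses mean titer. It is a worthwhile improvement, not a flaw that threatens a conclusion.

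**What to change.** In SAP 3.5.2, keep mean and CV% and add, for each antibody by visit and infusion-duration group:
- n, median, quartiles, minimum and maximum;
- geometric mean titer among antibody-positive samples, with a 95% CI computed on the log scale and back-transformed;
- the number of negative samples beside it, so that the geometric mean needs no substituted value.

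State whether negatives enter the mean and CV%, and with what value. Use the same statistics for anti-PEG titers at the last infusion and after treatment, where none are named.

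The cost is SAP wording and a few more rows in one table; the data are already collected. The downside is that a positives-only geometric mean must be read together with the proportion positive. In a cohort of about 10 with few positives its interval will be wide, or not computable with a single positive.

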### 3.6 Safety Analysis

#### 3.6.1 General Conventions

Unless otherwise specified, safety analyses will be based on the safety analysis set and the ITT analysis set, depending on the treatment period. The ITT analysis set will be used for analysis of safety data during the MTX Run-in Period prior to Day 1 and the safety analysis set will be used for analysis in the Pegloticase + MTX Period or summaries across both treatment periods. Summaries will be presented by “as-assigned” infusion duration group. Analyses done by “as-treated” group may be done, if warranted.

Refer to Section 3.1.6 for additional details regarding infusion duration group for reporting.

### 3.6.2 Extent of Exposure

Study drug exposure will be summarized by ‘as assigned’ infusion duration group for the following statistics: duration of treatment (in days), number of infusions (pegloticase only), and total dose received for MTX and pegloticase.

The usage of prophylaxis treatments (folic acid, IR usage of fexofenadine the day prior to pegloticase infusion, IR prophylaxis of fexofenadine and acetaminophen the morning prior to infusion, and IR prophylaxis of methylprednisolone immediately prior to infusion) will be provided in listings only. Reasons for infusion interruptions will be provided in the listings.

For the MTX Run-in Period, the following will be summarized using the ITT analysis set:

- Days in MTX Run-in Period
- Duration of treatment, defined as the Day 1 visit date – first dose date of MTX for subjects in the mITT analysis set and last dose of MTX – first dose of MTX + 1 for subjects who do not continue into the Pegloticase + MTX Treatment Period (summarized with descriptive statistics of mean, SD, median, minimum, and maximum)
- Total MTX dose taken between the first and last dose dates in the MTX Run-in Period, inclusive (in mg) (summarized with descriptive statistics of mean, SD, median, minimum, and maximum)
- Average weekly MTX dose (in mg) (total dosage for the MTX Run-in Period divided by number of doses taken during the MTX Run-in Period divided by [days in MTX Run-in Period / 7]) (summarized with descriptive statistics of mean, SD, median, minimum, and maximum)
- Number of subjects with MTX dosage reductions from planned 15 mg/week.

For the Pegloticase + MTX Period, the following will be summarized for the safety analysis set:

- Pegloticase
  - Days in Pegloticase + MTX Period
  - Duration of Pegloticase exposure in days defined as the last Pegloticase date – first Pegloticase dosing date + 1 (summarized with descriptive statistics of mean, SD, median, minimum and maximum)
  - Number of pegloticase infusions received (summarized with frequency summary and also with descriptive statistics of mean, SD, median, minimum, and maximum)
  - Duration of Pegloticase infusion in minutes
  - At least one planned infusion duration changed from assigned infusion duration
  - Proportion of subjects planned duration different from assigned infusion duration

- At each scheduled Pegloticase infusion visit the following will be summarized:
  - Number of subjects receiving a complete infusion (i.e. full dose administered)
  - Number of infusions administered without interruption
  - Number of subjects with an interrupted infusion
- MTX
  - Days in Pegloticase + MTX Period
  - Duration of MTX treatment during the Pegloticase + MTX Period, defined as the last MTX date – Day 1 visit date + 1, for dates occurring within the Pegloticase + MTX period
  - Total MTX dose (in mg) received during the Pegloticase + MTX period
  - Average weekly MTX dose (in mg) (total dose for the Pegloticase + MTX Period divided by number that patient's doses taken during the Pegloticase + MTX Period divided by [days in Pegloticase + MTX Period / 7])) (summarized with descriptive statistics of mean, SD, median, minimum, and maximum)
  - Number of subjects with MTX dosage reductions from planned 15 mg/week.

For the overall study, the following will be summarized using the safety analysis set:

- MTX
  - Days in study
  - Duration of MTX treatment, defined as the last MTX date – first MTX dosing date + 1
  - Cumulative MTX dose (in mg) received
  - Number of subjects with MTX dosage reductions from planned 15 mg/week.
  - Average weekly MTX dose (in mg) (average of each subject's total dose for the Pegloticase + MTX Period divided by number that patient's doses taken during the Pegloticase + MTX Period divided by [days in Pegloticase + MTX Period / 7])) (summarized with descriptive statistics of mean, SD, median, minimum, and maximum)

Subjects who had a dose adjustment/interruption of MTX due to tolerability issues will be listed.

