	Day 1	2	4	6	8	10	12	14	16	18	20	22							
MTX dosing calendar		X	X	X	X	X	X	X	X	X	X	X							
MTX dispensed 		X	X	X	X	X	X	X	X	X	X	X							
MTX dosing 		Once weekly from Week -4 to Week 23, one week after the Week 22 Visit, inclusive																	
Gout prophylaxis Rxs filled 		Rxs filled as needed, start taking at least one protocol standard gout flare prophylaxis regimen ≥1 week before first dose of pegloticase.																	
Fexofenadine Rx filled 			Rxs filled as needed, first dose of fexofenadine must be taken the day before D1; and in the morning or just prior to each infusion.																
Folic Acid Rx filled 		Rxs filled as needed, 1 mg orally every day beginning at Week -4.																	

Study Procedure/ Assessment	Screening	MTX Tolerability Assessment Period/ Run-in Period 		Pegloticase + MTX Period  Day 1 through Week 24											End-of- Pegloticase- Infusions Visit  (if applicable)	End-of- study/ Early Term.	Safety Follow-up	Post Treatment Follow- Up 
	Screening Visit  (35 d)	Week - 4 (±3 d)	Week - 2 (±3 d)	Week (±3 d)											Within 2 weeks following final infusion if prior to Wk 22	Wk 24 (±3 d)	30 days after last pegloticase infusion (±3 d)	3 Months
	Day 1	2	4	6	8	10	12	14	16	18	20	22						
IR prophylaxis 				X	X	X	X	X	X	X	X	X						
IR Rx prophylaxis compliance check (Yes/No)				X	X	X	X	X	X	X	X	X						
Gout flare prophylaxis compliance check (Yes/No)		X		X	X	X	X	X	X	X	X	X						
Pre-infusion MTX Polyglutamate sampling				X									X	X	X	X		
Pegloticase PK sampling 				X	X		X						X		X			
sUA 	X	X	X	X	X	X	X	X	X	X	X	X	X	X	X	X	X	
Hematology 	X 		X	X	X		X			X			X	X	X		X	

Study Procedure/ Assessment	Screening	MTX Tolerability Assessment Period/ Run-in Period 		Pegloticase + MTX Period  Day 1 through Week 24											End-of- Pegloticase- Infusions Visit  (if applicable)	End-of- study/ Early Term.	Safety Follow-up	Post Treatment Follow- Up 
	Screening Visit  (35 d)	Week - 4 (±3 d)	Week - 2 (±3 d)	Week (±3 d)											Within 2 weeks following final infusion if prior to Wk 22	Wk 24 (±3 d)	30 days after last pegloticase infusion (±3 d)	3 Months
	Day 1	2	4	6	8	10	12	14	16	18	20	22						
Chemistry	X		X	X	X		X			X			X	X	X		X	

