## 3 Statistical Methods

### 3.1 General Methods

Any changes to the finalized SAP made prior to database lock will be documented in an SAP amendment. Any changes to the planned analyses after database lock will be documented in the clinical study report (CSR).

Some of the analyses detailed here may be more explicit or in some aspects different from those stated in the protocol. In case of differences, this SAP supersedes the statistical sections in the protocol.

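### The average weekly MTX dose in SAP 3.6.2 is divided by the number of doses as well as by weeks, so it is not mg per week, and the overall-study row omits the run-in

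*SAP*

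**What the plan says.** SAP 3.6.2 (Extent of Exposure) lists an average weekly MTX dose, in mg, three times.

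- **Run-in, ITT set:** total run-in dosage "divided by number of doses taken during the MTX Run-in Period divided by [days in MTX Run-in Period / 7", with the bracket then closed.
- **Pegloticase + MTX Period, safety set:** the period total is divided by the number of "doses taken during the Pegloticase + MTX Period divided by [days in Pegloticase + MTX Period / 7".
- **Overall study, safety set:** the same double division, starting from the "average of each subject's total dose for the Pegloticase + MTX Period".

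The same lists include "Total MTX dose (in mg) received during the Pegloticase + MTX period" for the treatment period and "Cumulative MTX dose (in mg) received" for the overall study. They also count subjects reduced from a planned 15 mg per week, which is the natural benchmark for the row.

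**The concern.** An average weekly dose is total mg divided by weeks. A second division, by the number of doses, changes the unit. The extra divisor appears in all three rows, with different wording in the run-in row, so it does not look like a fault in reading the PDF. A programmer who follows the text would put a number under this label that contradicts the total-dose rows beside it and does not reflect missed doses. The overall-study row has a second fault. It is built from Pegloticase + MTX Period dose, dose count and days, so it would still leave out the run-in if the extra divisor were removed.

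**Working it through.** The SAP gives no numerical value for this row, so there is no stated figure to reproduce. The comparison is with the planned 15 mg per week.

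**Inputs**

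- Planned dose 15 mg weekly; run-in 4 weeks (28 days); Pegloticase + MTX Period 24 weeks (168 days): SAP 1.1.2, nominal lengths.
- MTX calendar, Protocol 2.1: "Once weekly from Week -4 to Week 23, one week after the Week 22 Visit, inclusive". That is 28 weekly doses, 28 × 15 = 420 mg.
- Split of the 28 doses between periods: four weeks of weekly dosing before pegloticase suggests 4 + 24. However, Protocol 9.5.2 places MTX 1 to 3 days, or at least 60 minutes, before each infusion, and SAP 1.6 ends the run-in at the date and time of the first pegloticase dose. The dose attached to Day 1 then falls in the run-in, giving 5 + 23. Both splits are shown.

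Let T = total mg, n = doses taken and w = days / 7.

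**As written, left to right: (T / n) / w, in mg per dose per week**

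- Run-in: 60/4/4 = 3.75; with 5 doses, 75/5/4 = 3.75.
- Treatment period, and overall row as written: 360/24/24 = 0.625; with 23 doses, 345/23/24 = 0.625.

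With unsplit 15 mg doses T/n is always 15, so the split does not matter.

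**Other grouping: T / (n / w), in mg·weeks per dose**

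- Run-in: 60/(4/4) = 60; 75/(5/4) = 60.
- Treatment period: 360/(24/24) = 360; 345/(23/24) = 360.

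**Check against the total-dose row:** 0.625 × 24 weeks = 15 mg, beside a total of 360 mg (345 mg with 23 doses).

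**Behaviour of the left-to-right value**

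- Half the doses missed (12 of 24): 180/12/24 = 0.625; T/w = 180/24 = 7.5.
- Full dose over 8 weeks: 120/8/8 = 1.875, against 0.625 over 24 weeks; T/w = 15 in both.
- Reduced to 10 mg throughout: 240/24/24 = 0.417. A change in dose size does move it.
- Split dosing (allowed in Protocol 9.5.2), if each BID intake counts as a dose: 60/8/4 = 1.875 and 360/48/24 = 0.3125.
- Period length ±3 days (assumed from the visit window): run-in 4.20 to 3.39 over 25 to 31 days; treatment 0.636 to 0.614 over 165 to 171 days.

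**Corrected: T / w, fully adherent subject**

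| | 4 + 24 | 5 + 23 |
|---|---|---|
| Run-in, 28 days | 60/4 = 15 | 75/4 = 18.75 |
| Treatment, 168 days | 360/24 = 15 | 345/24 = 14.4 |
| Overall, 196 days | 420/28 = 15 | 420/28 = 15 |

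In the 5 + 23 case, if the first dose comes 29 to 31 days before Day 1, the run-in value is 75/(29/7) = 18.1 to 75/(31/7) = 16.9.

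**Overall row, run-in omitted:** 60/420 = 14.3% of planned mg (4 + 24) or 75/420 = 17.9% (5 + 23). For a full run-in followed by 10 mg throughout, with the divisor deleted and 4 + 24 doses, whole-study inputs give (60 + 240)/28 = 10.7. The row's present inputs give 240/24 = 10.0, the same as the row above.

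**Day count for subjects who never receive pegloticase:** SAP 3.6.2 defines run-in duration "for subjects who do not continue into the Pegloticase + MTX Treatment Period" as last minus first MTX dose date plus 1. As a denominator here, that gives 15/(1/7) = 105 mg per week after one dose and 30/(8/7) = 26.25 after two.

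**The case against.** The strongest reply is that this is a drafting slip in a descriptive table. No endpoint, cohort decision or test uses the row. Total dose, duration and dose reductions are reported beside it, and MTX compliance has its own 80% rule in Protocol 9.5.11. A value of 0.625 mg would probably be noticed at output review. All of this stands, and it is why the severity is low. It does not make the definition right. The derivation is explicit, and programming something else would depart from it.

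It is also fair to say that urgency should not be overstated. SAP version 2.0 is already final, and SAP 3.1 says "Any changes to the finalized SAP made prior to database lock will be documented in an SAP amendment". Correcting the row now therefore does not avoid an amendment.

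A reader might infer three stronger things that the documents do not support:

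- That the corrected formula must return 15 in each period for a fully adherent subject. It does so only with a 4 + 24 split, and the pre-infusion timing of MTX points to 5 + 23.
- That 3.75 and 0.625 hold however doses are counted. They assume unsplit doses.
- That MTX exposure reporting as a whole is unsound. The neighbouring rows remain valid, and dose reductions do move even the faulty row.

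**Conclusion.** The point holds. Under neither grouping do the three rows give mg per week. Read left to right, they give 3.75 (run-in) and 0.625 (treatment period and overall) where the planned dose is 15 mg per week, assuming unsplit 15 mg doses and nominal 28- and 168-day periods. These values do not depend on how many doses are taken or on how the 28 scheduled doses divide between periods. Missed doses are invisible, and the value falls as the period lengthens. If days are counted to the End of Pegloticase visit, which SAP 1.6 permits, early discontinuers would show a higher figure than completers. The overall-study row separately duplicates the treatment-period row and leaves out the run-in. The effect is confined to three descriptive exposure rows.

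**What to change.** 1. In all three rows, delete the number-of-doses divisor: average weekly MTX dose = total MTX dose in the period (mg) / (days in the period / 7). This keeps the SAP's own denominator and removes any dependence on how split doses are counted.
2. In the overall-study row, use cumulative MTX dose / ((run-in days + Pegloticase + MTX Period days) / 7).
3. State how days are counted for early discontinuers and for subjects who never receive pegloticase. Do not use last minus first MTX dose date plus 1 for the latter. Whatever count is chosen must cover the week served by the last dose.
4. State to which period the MTX dose taken just before the first infusion belongs, so that period values near 18.75 and 14.4 are not misread as non-adherence or overdosing.

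The cost is three wording corrections and short clauses on day counting and dose allocation, carried in an SAP amendment if made before database lock, or described in the study report if later. No new data are needed.
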